Day (D)	D-20 to 0	D1 ^{b,pp}	D2	D3	D8 ^{pp}	D10	D15	D16	D19	D20	D26	D33	D40	D47	D54	D61	D64	D82		
Day (D)		D85	D86	D87	D92	D94	D99	D100	D103	D104	D110									
Central Laboratory Tests (continued)																				
Core or incisional/excisional lymph node biopsy for biomarker analysis (optional) ^{oo}	X ⁿⁿ																	X ⁿⁿ		
MRD by NGS (plasma) ^{oo}		X							X				X					X		

Page 3 of 3

AE = adverse event; CBC = complete blood count; CNS = central nervous system; CR = complete remission; CSF = cerebrospinal fluid; CT = computed tomography; DLBCL = diffuse large B-cell lymphoma; ECOG = Eastern Cooperative Oncology Group; FDG = fluorodeoxyglucose; FU = follow-up; HBc = hepatitis b core; HBs = hepatitis b surface; HBsAg = hepatitis b surface antigen; HBV = hepatitis b virus; HSCT = hematopoietic stem cell transplantation; IV = intravenous; LTFU = long-term follow-up; MRD = minimal residual disease; MRI = magnetic resonance imaging; MTD = maximum tolerated dose; NGS = next generation sequencing; PET = positron emission tomography; PK = pharmacokinetics; SAE = serious adverse event

^a Safety follow-up will occur 30 days (+7 days) after last dose of each protocol specified therapy. If a subject starts a new anti-lymphoma treatment within 30 days of their last dose of protocol-assigned therapy, a safety follow-up visit should be conducted immediately prior to starting any new treatment, including HSCT conditioning regimens.

^b All procedures completed on first day of study treatment must be completed prior to the initiation of protocol-required therapy.

^c The initial dose of blinatumomab will be 9 µg/day and the dose will be escalated at weekly intervals until the target dose is reached. See Figure 1. For subjects that experience a blinatumomab dose interruption during cycle 1, subjects should resume the schedule of assessments following D85-110 procedures on Table 7-3 at the start of cycle 2.

^d Pembrolizumab will be administered starting on study day 19 (21-day cycles). See Section 6.2.2. Pembrolizumab may be administered up to 3 days before or after each scheduled day 1 from pembrolizumab cycle 2 onwards. For pembrolizumab dosing past cycle 5, see Table 7-4.

^e Vital signs should be monitored continuously every 4 hours during the first 12 hours after the start of each new treatment/dose step.

^f Height to be measured at screening only. Weight to be measured at screening, baseline, and safety follow-up visit.

^g Recording of concomitant medication documentation during follow-up period **following the end of pembrolizumab monotherapy** is limited to only anti-lymphoma treatments, **plus any medications used for SAEs and ECIs that are reported according to protocol requirements.**

^h Report AEs occurring after enrollment **through the last safety follow-up visit that occurs 30 days (+7 days) following cessation of treatment. Report SAEs that occur after signing of the informed consent form through 90 days following cessation of treatment, or 30 days following cessation of treatment if the subject initiates new anticancer therapy, whichever is earlier. After this period, report SAEs suspected to be related to IP, and fatal SAEs regardless of causality.**

- ⁱ Available results of brain contrast-enhanced MRI (or CT if MRI contraindicated) performed up to 8 weeks prior to first day of study treatment are acceptable. In case of neurologic AE \geq grade 3 a brain MRI or CT should be performed.
- ^j If PET scans and CT scans are done separately, they must be within the \pm 3 day window and a maximum of 72 hours apart. If PET and CT are acquired on the same day, it is strongly recommended that PET is performed prior to the CT with IV contrast.
- ^k Enhanced MRI will be allowed to replace CT strictly when iodinated contrast is contraindicated.
- ^l Scans done within 28 days prior to first dose may be used in place of protocol-required assessments.
- ^m If PET scan at Screening is negative for disease involvement in the neck, screening and subsequent CT scans may not include neck. If PET scan at Screening is positive for disease involvement of the neck, subsequent CT scans must include neck.
- ⁿ After week 10 and during LTFU, subjects should have scans performed per the regular frequency every 12 weeks (\pm 3 days). PET/CTs should be performed until documented complete remission, progressive disease/relapse, or 24 months after the first assessment. Response assessment will also be conducted at the time of treatment discontinuation due to clinically suspected disease progression/relapse. In case of suspected pseudo-progression/relapse, repeat imaging performed 4 to 8 weeks from initial assessment suspicious for PD/relapse. Subjects who receive at least 1 full dose of pembrolizumab who discontinue from all study treatment in cycle 1, for whatever reason, shall undergo a PET/CT scan between 14 to 28 days after last pembrolizumab exposure.
- ^o For lymphomas that are not FDG-avid at screening, PET does not need to be repeated in follow-up assessments.
- ^p Lumbar puncture and bone marrow biopsy performed up to 49 days prior to enrollment may be used in place of protocol-required assessments. An assessment of the CSF will be performed at screening if there is a concern of CNS lymphoma involvement or during treatment period if subject has a seizure. Cerebrospinal fluid, cell count, glucose, and protein will be measured at the local laboratory as part of the examination to ensure that no infiltration of the CSF by DLBCL is present. Additional investigations of the CSF should be performed as clinically appropriate.
- ^q Bone marrow biopsy is not required if PET scan is negative in marrow and if not otherwise clinically necessary by investigator discretion.
- ^r Bone marrow biopsy only required to be repeated with response assessments in case of infiltration or unclear results at screening and in order to confirm a CR.
- ^s Anti pembrolizumab antibodies, pembrolizumab PK samples, thyroid function tests, chemistry, Hematology/CBC and urinalysis will be collected on the same day as pembrolizumab administration, which may be up to 3 days before or after each scheduled day 1 from pembrolizumab cycle 2 onwards.
- ^t Immunoglobulins to be collected predose at day 1.
- ^u Thyroid function tests must be collected, but if there are no symptoms of hypothyroidism or hyperthyroidism, study treatment can be initiated prior to the reporting of the laboratory results. Thyroid function testing done at screening, the first day of pembrolizumab cycle 1 (study day 19), and then every 2 pembrolizumab cycles thereafter. Refer to [Table 7-4](#).
- ^v Done at pembrolizumab safety follow-up visit only.
- ^w Hepatitis B antibodies tested at screening only; HBV viral load done at screening and at regular intervals starting at day 8 only for subjects with indeterminate HBV status (specifically for indeterminate core antibody positive, surface antibody negative, and surface antigen negative).
- ^x Done at day 85 only.
- ^y Monthly pregnancy testing should be conducted as per local regulations where applicable. Screening pregnancy test to be done within 72 hours prior to receiving the first dose of study medication.
- ^z Blinatumomab anti-drug antibodies (serum) samples are collected at day 1 (pre-dose), D40, and safety follow-up.
- ^{aa} Done at blinatumomab safety follow-up only.
- ^{bb} Pembrolizumab anti-drug antibodies (serum) will be collected at predose (trough) within 24 hours before the following infusions of pembrolizumab: 1 (study day 19), 2 (study day 40), 4 (study day 82), 6 (study day 124), 8 (study day 166), and every 4 infusions thereafter, until 30 days after discontinuation of pembrolizumab (or until the subject starts new anticancer therapy) ([Table 7-4](#)).
- ^{cc} Done only on the first day of pembrolizumab cycle 1 (study day 19).
- ^{dd} Immune panel assessments only performed during cycle 1, and collected on days 1, 2, 3, 8, 15, 16, 19, 20, 26, 33, 40, 61, and 64. Sample collection for the Immune and Cytokine panels on days 1-16 corresponds to blinatumomab exposure, while days 19-64 corresponds to pembrolizumab exposure.
- ^{ee} Immune panel must be drawn after dexamethasone premedication but no more than 15 minutes before initiation of blinatumomab therapy.

- ^{ff} Cytokines must be drawn after dexamethasone premedication but no more than 15 minutes before initiation of blinatumomab therapy. In the case of clinically relevant CRS or neurotoxicity, samples should be collected at baseline (onset of CRS or neurotoxicity), 48 hr, and 72 hrs after onset. If event not resolved by 72 hr, collect an additional sample at the time of resolution. Sample collection for the Immune and Cytokine panels on days 1-16 corresponds to blinatumomab exposure, while days 19-64 corresponds to pembrolizumab exposure.
- ^{gg} Blood samples for cytokine measurement will be collected for cycles 1 and 2 only. For D1, cytokine measurements will be collected on C1D1 and C2D1 (D85).
- ^{hh} Blood samples for cytokine measurements during cycle 2, but not cycle 1, will be collected on C2D2 (D86) and C2D3 (D87).
- ⁱⁱ Blood samples for cytokine measurements will be collected on C1D15 prior to start of blinatumomab 56 µg/d infusion in cohort IIa or 112 µg/d in cohort IIIa, and 2 and 6 hours after the start of blinatumomab infusion, and on C1D19 prior to the start of pembrolizumab infusion, and 2 and 6 hours post end of pembrolizumab infusion.
- ^{jj} Blood samples for blinatumomab PK measurement will be taken at D1 (predose, 4, 6, 8 h after start of 9 µg/d infusion), D2 (any time), D8 (6-10 h after start of 28 µg/d infusion), D10 (any time), D15 (prior to start of 56 µg/d infusion in cohort IIa or 112 µg/d in cohort IIIa and 2 hours and 6 hours after the start of infusion of blinatumomab), D19 (1 h after pembrolizumab infusion has ended), D26 (any time) and D40 (any time) in blinatumomab cycle 1 (see Section 7.3.14.1). In the expansion cohort, blinatumomab PK samples will be collected on D2 (any time), D10 (any time), D22 (any time), and D29 (any time) in cycle 1. Pharmacokinetic samples must be drawn from a site that is distal to the site where the investigational product has been administered to avoid contamination of the PK samples and to better estimate PK parameters.
- ^{kk} Blood samples for pembrolizumab PK predose samples (serum) will be collected within 24 hours before the following infusions of pembrolizumab: on the first day of pembrolizumab treatment (study day 19) and at pembrolizumab cycles 2 (study day 40), 4 (study day 82), 6 (study day 124), and 8 (study day 166), then every 4 cycles (see Section 7.3.14.2).
- ^{ll} The first dose of pembrolizumab must be delayed if blinatumomab is interrupted during the step dose period per protocol (see Table 6-1). The first dose of pembrolizumab can only be given after the blinatumomab target dose is reached (+ 4 days); also, before adding pembrolizumab, there should be no blinatumomab dose interruption due to adverse events, no > grade 1 CRS and/or neurologic events.
- ^{mmm} Pembrolizumab PK postdose samples will be collected 30 minutes post infusion on the first day of pembrolizumab treatment (study day 19), then on days 2 (study day 20), 8 (study day 26), and 15 (study day 33) of pembrolizumab cycle 1, then 30 minutes post-infusion on cycle 8 day 1 (study day 166), and 30 days after discontinuation of pembrolizumab (see Section 7.3.14.2).
- ⁿⁿ If available and consented to, submission of formalin-fixed paraffin embedded tumor tissue sample blocks are preferred; slides or fresh frozen tissue are acceptable. Second biopsy to be collected only in subjects who consent to additional biopsies.
- ^{oo} For MRD analysis a tumor lymph node biopsy and plasma samples will be collected if optional consent is signed. A tumor lymph node biopsy (optional) will be collected at screening, or (when available) archival tissue collected up to 3 months prior to first day of study treatment is acceptable. Plasma samples will be collected on days 1, 19, and 40 pre-dose, and at week 10 (ie, D64), that corresponds to when a subject comes in for disease response assessment, or time of first disease response assessment if done prior to week 10 for cycles 1-2 only. Note: If no lymph node biopsy tissue is collected, then no plasma samples should be collected.
- ^{pp} If blinatumomab is interrupted per Table 6-1, the schedule of assessments will need to be repeated to align with blinatumomab dose. If re-starting at 9 µg/d repeat schedule of assessment procedures starting at D1. If re-starting at 28 µg/d repeat schedule of assessment procedures starting at D8.
- ^{qq} **Serious DREs will be reported through 90 days following cessation of treatment, or 30 days following cessation of treatment if the subject initiates new anticancer therapy (whichever is earlier). Additionally, the investigator must report all fatal DREs.**

**Table 7-4. Schedule of Pembrolizumab Dosing and Related Assessments For Cohorts IIa and IIIa
 (And For Part 2 if MTD is Reached in Either of These Cohorts)**

Pembro- lizumab Cycle	Week	Study Day ^a	Pembrolizumab Dosing ^a	Anti-Pembrolizumab- Antibodies ^b	Pembrolizumab- PK Predose ^c	Pembrolizumab PK Postdose ^d	Thyroid function tests ^e	Chemistry ^e	Hematology/CBC ^e	Urinalysis ^e
Screening	-3 to- 1	-20 to 0					x	x	x	x
Cycle 1	3	19	x	x	x	x	x	x	x	x
Cycle 2	6	40	x	x	x			x	x	
Cycle 3	9	61	x				x	x	x	x
Cycle 4	12	82	x	x	x			x	x	
Cycle 5	15	103	x				x	x	x	x
Cycle 6	18	124	x	x	x			x	x	
Cycle 7	21	145	x				x	x	x	x
Cycle 8	24	166	x	x	x	x		x	x	
Cycle 9	27	187	x				x	x	x	x
Cycle 10	30	208	x					x	x	
Cycle 11	33	229	x				x	x	x	x
Cycle 12	36	250	x	x	x			x	x	
Cycle 13	39	271	x				x	x	x	x
Cycle 14	42	292	x					x	x	
Cycle 15	45	313	x				x	x	x	x
Cycle 16	48	334	x	x	x			x	x	
Cycle 17	51	355	x				x	x	x	x
Cycle 18	54	376	x					x	x	
Cycle 19	57	397	x				x	x	x	x
Cycle 20	60	418	x	x	x			x	x	
Cycle 21	63	439	x				x	x	x	x
Cycle 22	66	460	x					x	x	
Cycle 23	69	481	x				x	x	x	x
Cycle 24	72	502	x	x	x			x	x	
Cycle 25	75	523	x				x	x	x	x
Cycle 26	78	544	x					x	x	
Cycle 27	81	565	x				x	x	x	x

Footnotes defined on the next page of the table

**Table 7-4. Schedule of Pembrolizumab Dosing and Related Assessments For Cohorts IIa and IIIa
 (And For Part 2 if MTD is Reached in Either of These Cohorts)**

Pembro- lizumab Cycle	Week	Study Day ^a	Pembrolizumab Dosing ^a	Anti-Pembrolizumab- Antibodies ^b	Pembrolizumab- PK Predose ^c	Pembrolizumab PK Postdose ^d	Thyroid function tests ^e	Chemistry ^e	Hematology/CBC ^e	Urinalysis ^e
Cycle 28	84	586	x	x	x			x	x	
Cycle 29	87	607	x				x	x	x	x
Cycle 30	90	628	x					x	x	
Cycle 31	93	649	x				x	x	x	x
Cycle 32	96	670	x	x	x			x	x	
Cycle 33	99	691	x				x	x	x	x
Cycle 34	102	712	x					x	x	
Cycle 35	105	733	x				x	x	x	x
Safety FU	109	763		x		x	x	x	x	x

Page 2 of 2

CBC = complete blood count; FU = follow-up; MTD = maximum tolerated dose; PK = pharmacokinetic

^a Pembrolizumab may be administered up to 3 days before or after each scheduled day 1 from pembrolizumab cycle 2 onwards. The first dose of pembrolizumab must be delayed if blinatumomab is interrupted during the step dose period per protocol (see [Table 6-1](#)). The first dose of pembrolizumab can only be given after the blinatumomab target dose is reached (+ 4 days); also, before adding pembrolizumab, there should be no blinatumomab dose interruption due to adverse events, no > grade 1 CRS and/or neurologic events.

^b Pembrolizumab anti-drug antibodies (serum) will be collected at predose (trough) within 24 hours before the following infusions of pembrolizumab: 1 (study day 19), 2 (study day 40), 4 (study day 82), 6 (study day 124), 8 (study day 166), and every 4 infusions thereafter, and 30 days after discontinuation of pembrolizumab (or until the subject starts new anticancer therapy).

^c Pembrolizumab PK predose samples (serum) will be collected within 24 hours before the following infusions of pembrolizumab: on the first day of pembrolizumab treatment (study day 19) and at pembrolizumab cycles 2 (study day 40), 4 (study day 82), 6 (study day 124), and 8 (study day 166), then every 4 cycles. Refer to [Table 7-3](#).

^d PK postdose samples will be collected 30 minutes post infusion on the first day of pembrolizumab treatment (study day 19), then on days 2 (study day 20), 8 (study day 26), and 15 (study day 33) of pembrolizumab cycle 1: then 30 minutes post-infusion on cycle 8 day 1 (study day 166), and 30 days after discontinuation of pembrolizumab. Refer to [Table 7-3](#).

^e Anti pembrolizumab antibodies, pembrolizumab PK samples, thyroid function tests, chemistry, Hematology/CBC and urinalysis will be collected on the same day as pembrolizumab administration, which may be up to 3 days before or after each scheduled day 1 from pembrolizumab cycle 2 onwards.

Refer to the applicable supplemental laboratory **manual** for detailed collection and handling procedures.

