
Subjects who have been dose reduced will have an option to re-escalate to higher dose levels within their assigned dose cohort once the adverse event has resolved to grade 1 or less for at least 7 days. (See [Appendix F](#)).

Re-start of the infusion should be performed in the hospital, under supervision of the investigator. Before blinatumomab is re-started, premedication with dexamethasone must be administered as described in [Table 6-4](#). The subject should be observed overnight for possible side effects after each restart, either in the hospital or in the outpatient setting, as applicable. When the blinatumomab infusion is re-started per [Table 6-1](#) guidelines, the schedule of assessment procedures should be repeated to align with the re-started blinatumomab dose. If re-start is at 9 µg/d then repeat schedule of assessments starting at D1. If re-start is at 28 µg/d then repeat schedule of assessments starting at D8. Refer to [Table 7-1](#) and [Table 7-2](#) for cohort Ia and [Table 7-3](#) and [Table 7-4](#) for cohort IIa/IIIa. In addition, at the start of blinatumomab cycle 2, subjects should resume the schedule of assessments following D85 to D110 procedures as outlined in [Table 7-1](#) for cohort Ia and [Table 7-3](#) for cohort IIa/IIIa (exception is for pembrolizumab specific tests which are referenced in [Table 7-2](#) and [Table 7-4](#)).

In addition to the events described above, the dose may be temporarily or permanently reduced if, by investigator's judgment, it is necessary for safety reasons.

After at least 7 days of dosing at the reduced level, the dose may be increased back to the next higher dose level. An infusion interruption of more than 14 days due to an adverse event related to blinatumomab will lead to permanent discontinuation of treatment. In case of logistical difficulties, restart of treatment can be postponed for up to 7 additional days without resulting in permanent treatment discontinuation. Treatment may be also interrupted or permanently discontinued at the discretion of the investigator if any clinical/laboratory adverse event is considered to be medically relevant.

In case of signs of cytokine release, dexamethasone must be administered orally or IV at a dose of at maximum 3 x 8 mg/day for up to 72 hours.

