
Footnotes defined on the last page of the table

**Table 7-1. Schedule of Assessments for Cohort 1a
 (And for Part 2 if MTD is Reached in Cohort 1a)**

Blinatumomab Cycles	Screening	Treatment Period: cycle 1 (days 1 – 57) Blinatumomab Infusion cycle 2 (days 85- 113) Blinatumomab Infusion														Blinatumomab Treatment Free Period (days 58-84)	Safety FU ^a	LTFU Efficacy/ Survival
Pembrolizumab Cycles	Screening	Pembrolizumab cycles 1 - 3														Pembrolizumab cycle 4	30 days (+7 days) after last dose	Every 12 weeks (±28 days)
		Pembrolizumab cycle 5 [After cycle 5: continued Pembrolizumab cycles every 21 days (Table 7-2)]																
Day (D)	D-20 to D0	D1 ^{b,II}	D2	D3	D8 ^{II}	D10	D15	D16	D22	D29	D36	D43	D50	D57	D64	D78		
Day (D)		D85	D86	D87	D92	D94	D99	D100	D106	D113								
Local Laboratory Tests (continued)																		
HBsAg, anti-HBc, anti-HBs (screening only) and HBV viral load ^w	X	X ^x			X		X		X	X	X	X	X	X	X	X		
Pregnancy Test ^y	X																	
Central Laboratory Tests																		
Anti-Blinatumomab antibodies ^z		X										X					X ^{aa}	
Anti-Pembrolizumab antibodies ^{s, bb}							X ^{cc}				X					X	X ^v	
Immune panel ^{dd, ee}		X	X	X	X	X			X			X			X			

Footnotes defined on the last page of the table

**Table 7-1. Schedule of Assessments for Cohort 1a
 (And for Part 2 if MTD is Reached in Cohort 1a)**

Blinatumomab Cycles	Screening	Treatment Period: cycle 1 (days 1 – 57) Blinatumomab Infusion cycle 2 (days 85- 113) Blinatumomab Infusion													Blinatumomab Treatment Free Period (days 58-84)	Safety FU ^a	LTFU Efficacy/ Survival	
Pembrolizumab Cycles	Screening	Pembrolizumab cycles 1 - 3													Pembrolizumab cycle 4	30 days (+7 days) after last dose	Every 12 weeks (±28 days)	
		Pembrolizumab cycle 5 [After cycle 5: continued Pembrolizumab cycles every 21 days (Table 7-2)]																
Day (D)	D-20 to D0	D1 ^{b,ii}	D2	D3	D8 ⁱⁱ	D10	D15	D16	D22	D29	D36	D43	D50	D57	D64	D78		
Day (D)		D85	D86	D87	D92	D94	D99	D100	D106	D113								
Central Laboratory Tests (continued)																		
Serum cytokines ^{ff, ii}		X	X	X	X		X		X									
PK Sample (Blinatumomab) ^{gg}		X	X		X	X	X		X	X		X						
PK Sample predose (Pembrolizumab) ^{s, hh, ii}							X ^{cc}				X				X			
PK Sample postdose (Pembrolizumab) ^{s, ii, ij}							X	X	X	X						X ^v		
Core or incisional/excisional biopsy for biomarker analysis	X ^{kk}														X ^{kk}			
MRD by NGS	X														X			

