AE = adverse event; CBC = complete blood count; CNS = central nervous system; CR = complete remission; CRS = cytokine release syndrome; CSF = cerebrospinal fluid; CT = computed tomography; DLBCL = diffuse large B-cell lymphoma; ECOG = Eastern Cooperative Oncology Group; FDG = fluorodeoxyglucose; FU = follow up; HBc = hepatitis b core; HBs = hepatitis b surface; HBsAg = hepatitis b surface antigen; HBV = hepatitis b virus; HSCT = hematopoietic stem cell transplantation; IV = intravenous; LTFU = long-term follow-up; MRD = minimal residual disease; MRI = magnetic resonance imaging; MTD = maximum tolerated dose; NGS = next generation sequencing; PET = positron emission tomography; PK = pharmacokinetics; SAE = serious adverse event

^a Safety follow-up will occur 30 days (+7 days) after last dose of each protocol specified therapy. If a subject starts a new anti-lymphoma treatment within 30 days of their last dose of protocol-assigned therapy, a safety follow-up visit should be conducted immediately prior to starting any new treatment, including HSCT conditioning regimens.

^b All procedures completed on first day of study treatment must be completed prior to the initiation of protocol-required therapy. Subjects should initiate protocol-specified therapy within 5 days of enrollment confirmation.

^c The initial dose of blinatumomab will be 9 µg/day and the dose will be escalated at weekly intervals until the target dose is reached. See Figure 1. For subjects that experience a blinatumomab dose interruption during cycle 1, subjects should resume the schedule of assessments following D85-110 procedures on Table 7-3 at the start of cycle 2.

^d Pembrolizumab will be administered starting on study day 15 (21-day cycles). See Section 6.2.2. Pembrolizumab may be administered up to 3 days before or after each scheduled day (calculated from Day 1) from pembrolizumab cycle 2 onwards. For pembrolizumab dosing past cycle 5, see Table 7-2.

^e Vital signs should be monitored continuously every 4 hours during the first 12 hours after the start of each new treatment/dose step.

^f Height to be measured at screening only. Weight to be measured at screening, baseline, and safety follow-up visit.

^g Recording of concomitant medication documentation during follow-up period **following the end of pembrolizumab monotherapy** is limited to only anti-lymphoma treatments, **plus any medications used for SAEs and ECIs that are reported according to protocol requirements.**

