^p Lumbar puncture and bone marrow biopsy performed up to 49 days prior to enrollment may be used in place of protocol-required assessments. An assessment of the CSF will be performed at screening if there is a concern of CNS lymphoma involvement or during treatment period if subject has a seizure. Cerebrospinal fluid, cell count, glucose, and protein will be measured at the local laboratory as part of the examination to ensure that no infiltration of the CSF by DLBCL is present. Additional investigations of the CSF should be performed as clinically appropriate.

^q Bone marrow biopsy is not required if PET scan is negative in marrow and if not otherwise clinically necessary by investigator discretion.

^r Bone marrow biopsy only required to be repeated with response assessments in case of infiltration or unclear results at screening and in order to confirm a CR.

^s Anti-pembrolizumab antibodies, pembrolizumab PK samples, thyroid function tests, chemistry, hematology/CBC, and urinalysis will be collected on the same day as pembrolizumab administration, which may be up to 3 days before or after each scheduled day 1 from pembrolizumab cycle 2 onwards.

^t Immunoglobulins to be collected predose at day 1.

^u Thyroid function tests must be collected, but if there are no symptoms of hypothyroidism or hyperthyroidism, study treatment can be initiated prior to the reporting of the laboratory results. Thyroid function testing done at screening, the first day of pembrolizumab cycle 1 (study day 15), and then every 2 pembrolizumab cycles thereafter. Refer to [Table 7-2](#).

^v Done at pembrolizumab safety follow-up visit only.

^w Hepatitis B antibodies tested at screening only; HBV viral load done at screening and at regular intervals starting at day 8 only for subjects with indeterminate HBV status (specifically for indeterminate core antibody positive, surface antibody negative, and surface antigen negative).

^x Done on day 85 only.

^y Monthly pregnancy testing should be conducted as per local regulations where applicable. Screening pregnancy test to be done within 72 hours prior to receiving the first dose of study medication.

^z Blinatumomab anti-drug antibodies (serum) samples are collected at day 1 (pre-dose), D43, and safety follow-up.

^{aa} Done at blinatumomab safety follow-up visit only.

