^{bb} Pembrolizumab anti-drug antibodies (serum) will be collected at predose (trough) within 24 hours before the following infusions of pembrolizumab: 1 (study day 15), 2 (study day 36), 4 (study day 78), 6 (study day 120), 8 (study day 162), and every 4 infusions thereafter, until 30 days after discontinuation of pembrolizumab (or until the subject starts new anticancer therapy [[Table 7-2](#)]).

^{cc} Done only on the first day of pembrolizumab cycle 1 (study day 15).

^{dd} Immune panel must be drawn after dexamethasone premedication but no more than 15 minutes before initiation of blinatumomab therapy.

^{ee} Immune panel assessments only performed in blinatumomab cycle 1.

^{ff} Blood samples for cytokine measurement will be taken in blinatumomab cycle 1 only. Cytokines must be drawn after dexamethasone premedication but no more than 15 minutes before initiation of blinatumomab therapy.

^{gg} Blood samples for blinatumomab PK measurement will be taken at D1 (predose, 4, 6, 8 h after start of 9 µg/d infusion), D2 (any time), D8 (6-10 h after start of 28 µg/d infusion), D10 (any time), D15 (1 h after pembrolizumab has ended), D22 (any time), D29 (any time) and D43 (any time) in blinatumomab cycle 1 (see [Section 7.3.14.1](#)). In the expansion cohort, blinatumomab PK samples will be collected on D2 (any time), D10 (any time), D22 (any time), and D29 (any time) in cycle 1. If drug was administered via a central venous catheter, the PK sample collection should be from a peripheral site to avoid contamination of the PK samples and to better estimate PK parameters.

^{hh} Blood samples for pembrolizumab PK predose samples (serum) will be collected within 24 hours before the following infusions of pembrolizumab: on the first day of pembrolizumab treatment (study day 15), cycles 2 (study day 36), 4 (study day 78), 6 (study day 120), and 8 (study day 162), then every 4 cycles (see [Section 7.3.14.2](#)).

ⁱⁱ The first dose of pembrolizumab must be delayed if blinatumomab is interrupted during the step dose period per protocol (see [Table 6-1](#)). The first dose of pembrolizumab can only be given after the blinatumomab target dose is reached (+ 4 days); also, before adding pembrolizumab, there should be no blinatumomab dose interruption due to adverse events, no > grade 1 CRS and/or neurologic events.

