^e Anti-pembrolizumab antibodies, pembrolizumab PK samples, thyroid function tests, chemistry, hematology/cbc, and urinalysis will be collected on the same day as pembrolizumab administration, which may be up to 3 days before or after each scheduled day 1 from pembrolizumab cycle 2 onwards.

**Table 7-3. Schedule of Assessments for Cohort IIa and IIIa
 (And for Part 2 if MTD is Reached in Either of These Cohorts)**

Blinatumomab Cycles	Screening	Treatment Period: cycle 1 (days 1 - 57) Blinatumomab Infusion cycle 2 (days 85 - 113) Blinatumomab Infusion														Blinatumomab Treatment Free Period (days 58 – 84)			Safety FU ^a	LTFU Efficacy/ Survival
Pembrolizumab Cycles	Screening	Pembrolizumab cycles 1-2 Pembrolizumab cycle 5 [After cycle 5: Continued Pembrolizumab cycles every 21 days] (Table 7-4)														Pembrolizumab cycle 3-4			30 days (+ 7 days) after last dose	Every 12 weeks (± 28 days)
Day (D)	D-20 to 0	D1 ^{b,pp}	D2	D3	D8 ^{pp}	D10	D15	D16	D19	D20	D26	D33	D40	D47	D54	D61	D64	D82		
Day (D)		D85	D86	D87	D92	D94	D99	D100	D103	D104	D110									
Protocol-Required Therapy Administration																				
Blinatumomab ^c		X	X	X	X	X	X	X	X	X	X	X	X	X	X					
Pembrolizumab ^d									X				X			X	X			
General Assessments																				
Informed Consent	X																			
Inclusion/Exclusion Criteria	X																			
Demographics	X																			
Medical History/Current Medical Condition	X																			
ECOG Performance Status	X																		X	
Vital signs	X	X ^e	X	X	X ^e	X	X ^e		X		X	X	X	X	X				X	
Physical Examination (including neurological examination)	X	X			X		X		X		X	X	X	X	X				X	
Height & Weight ^f	X	X																	X	
Concomitant Medication	X	Continuously throughout the study																	X ^g	
AE/SAE Assessment	X ^h	Continuously throughout the study																	X ^h	
Disease Related Events		Continuously throughout the study																	X ^{gg}	
Radiologic Assessments																				
Brain MRI ⁱ	X																			
CT scan ^{j,k}	X ^{l,m}																	X ^{m,n}	X ^{m,n}	
PET scan ^j	X ^l																	X ^{n,o}	X ^{n,o}	

Footnotes defined on the last page of the table

**Table 7-3. Schedule of Assessments for Cohort IIa and IIIa
 (And for Part 2 if MTD is Reached in Either of These Cohorts)**

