7.3.7 Hepatitis B Antigen, Anti-Hepatitis B core Antigen, and Anti-Hepatitis B Surface Antigen

Hepatitis b surface (HBs) antigen, HBs antibody, and hepatitis b core (HBc) antibody will be tested at screening for all subjects. For subjects with history of seronegative HBV exposure or indeterminate HBV status (anti-Hbc antibody positive, anti-HBs antibody negative, and anti-HBs antigen negative), HBV DNA viral load should be performed at screening and at regular intervals during blinatumomab treatment to monitor for HBV re-activation.

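### Table 7-1 footnote c sends cohort Ia to the cohort IIa/IIIa schedule (Table 7-3) for cycle 2, and Section 6.2.1.4.1 names the right table but an end-day, D110, that Table 7-1 does not contain

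*Protocol*

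**What the plan says.** Two places in the protocol say which assessments apply in cycle 2 after a cycle 1 interruption of blinatumomab.

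- **Table 7-1, footnote c.** Table 7-1 covers cohort Ia, and Part 2 if run at that dose. The footnote directs interrupted subjects to resume "following D85-110 procedures on Table 7-3 at the start of cycle 2". Footnote c of Table 7-3 carries the same sentence, and there the reference is correct.
- **Section 6.2.1.4.1.** For the start of cycle 2 the text reads "subjects should resume the schedule of assessments following D85 to D110 procedures as outlined in". The rest of that sentence assigns cohort Ia to Table 7-1 and cohorts IIa/IIIa to Table 7-3. Pembrolizumab-specific tests are excepted and sent to Tables 7-2 and 7-4. One day range serves both tables.

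The title of Table 7-3 limits it to the other cohorts: "Schedule of Assessments for Cohort IIa and IIIa", plus Part 2 if the MTD is reached in one of them.

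Two kinds of sampling differ between the tables in cycle 2:

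- **HBV viral load.** Table 7-1 footnote w has "HBV viral load done at screening and at regular intervals starting at day 8 only for subjects with indeterminate HBV status". Section 7.3.7 gives the purpose: testing "at regular intervals during blinatumomab treatment to monitor for HBV re-activation".
- **Serum cytokines.** Table 7-1 footnote ff says "Blood samples for cytokine measurement will be taken in blinatumomab cycle 1 only". Table 7-3 footnote gg says "Blood samples for cytokine measurement will be collected for cycles 1 and 2 only".

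**The concern.** The two instructions send the same cohort Ia subjects to different tables for monitoring while they are re-exposed to blinatumomab. Footnote c names the wrong table outright; it is not merely vague, and sites work from the schedule and its footnotes. Section 6.2.1.4.1 names the right table but attaches an end-day that this table lacks. A site using footnote c would run some safety checks on the wrong days, do one HBV viral load check fewer in the subjects it is meant for, and draw blood for cytokines that the cohort Ia schedule does not ask for. Later, a reviewer of deviations could not tell from footnote c alone which schedule had applied.

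**Working it through.** No statistical figure is involved. The check sets the cycle 2 columns and rows of the two tables side by side.

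**1. Cycle 2 days.**

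| Table | Cohort | Cycle 2 columns |
|---|---|---|
| 7-1 | Ia | D85, 86, 87, 92, 94, 99, 100, **106, 113** |
| 7-3 | IIa/IIIa | D85, 86, 87, 92, 94, 99, 100, **103, 104, 110** |

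The tables share seven days. D106 and D113 occur only in Table 7-1; D103, D104 and D110 only in Table 7-3.

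**2. Section 6.2.1.4.1 applied to Table 7-1.** The Table 7-1 columns from D85 to D110 end at D106. Read literally, the range leaves out the D113 visit, although the table header runs the cycle 2 infusion to day 113.

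**3. Footnote c applied to cohort Ia: visits.** D106 becomes D103 (106 − 103 = 3 days earlier) and D113 becomes D110 (113 − 110 = 3 days earlier). Vital signs, physical and neurological examination, chemistry, coagulation and hematology are marked at both visits in either table, so this substitution loses none of them.

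**4. Footnote c: HBV viral load.** From the row for "anti-HBs (screening only) and HBV viral load" in each table:

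- Table 7-1: D85, 92, 99, 106, 113. That is 5 checks, with gaps of 7, 7, 7 and 7 days.
- Table 7-3: D85, 92, 99, 110, with D103 and D104 blank. That is 4 checks, with gaps of 7, 7 and 110 − 99 = 11 days.

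The difference is 5 − 4 = 1 check, and the longest gap is 11 days against 7. This concerns only subjects with indeterminate HBV status.

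**5. Footnote c: cytokines.** Table 7-1 footnote ff allows none in cycle 2. Table 7-3 footnotes gg and hh require D85, D86 and D87, so at least three sampling days are added. The Table 7-3 cytokine row also marks the columns for D92, D100 and D104 with no footnote confining those marks to cycle 1. Three is therefore a minimum, not an exact count.

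**6. Cross-check on cytokines.** Section 7.5.2 lists only days 1, 2, 3, 8, 15 and 22 for cohort Ia, which agrees with footnote ff. Its cycle 2 sentence (days 85, 86 and 87) follows the sentence on cohorts IIa and IIIa but names no cohort.

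**The case against.** The strongest reply is that the protocol largely corrects itself. Section 6.2.1.4.1 is the operative section on interruptions and assigns Table 7-1 to cohort Ia. Its evident purpose is to say where subjects rejoin the calendar, and a shared end-day need not cancel a marked D113 column. Table 7-3 is titled for other cohorts, and some of its footnotes refer to 56 and 112 µg/day, which cohort Ia does not receive. This stands in large part. A reader might infer that cohort Ia has no correct instruction anywhere; the documents do not support that, because Section 6.2.1.4.1 gives the right table and errs only in the end-day.

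The HBV count can also be challenged because it rests on blank cells, and in the text copy of Table 7-3 some marks have shifted. The fourth pembrolizumab dose appears under D64, whereas Table 7-4 puts it on D82. The shifts seen lie in the right-hand columns, outside the cycle 2 days, so they do not overturn the count, but the count should be given as read from the text copy. Nor is the 11-day gap a breach of a stated interval: footnote w and Section 7.3.7 ask for regular testing and fix no number of days.

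Reach may be zero. It takes a cohort Ia subject who was interrupted in cycle 1 and then started cycle 2; the HBV effect also needs indeterminate HBV status, and exclusion criterion 222 already removes anyone with a quantifiable viral load. The Amendment 5 summary mentions a schedule adjustment after blinatumomab interruption. If footnote c came in then, cohort Ia may never have been governed by it, but the documents do not say.

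**Conclusion.** The cross-reference is wrong as written, and the point is minor. Footnote c of Table 7-1 cites another cohort group's schedule, probably copied from Table 7-3. Section 6.2.1.4.1 names the correct table but gives cohort Ia an end-day belonging to Table 7-3.

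Under a literal reading of footnote c, two visits move 3 days earlier, one of five cycle 2 HBV checks is lost for indeterminate-HBV subjects, and at least three cytokine sampling days are added. The HBV figures assume that the table cells read correctly in the text copy. The cytokine point rests mainly on footnote ff, since the cycle 2 sentence in Section 7.5.2 names no cohort.

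A reader might also infer harm to the trial's results. The documents do not support that: no DLT, response or survival endpoint depends on these entries, and design, sample size and stopping boundaries are untouched. Part 1 allows at most 10 subjects in cohort Ia, apart from replacements. Only those interrupted in cycle 1 who start cycle 2 are concerned, and the documents do not show how many there are. SAP Section 11 records that Part 2 did not go ahead, so the reach does not extend to an expansion cohort.

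**What to change.** Make two edits:

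- **Table 7-1, footnote c:** refer to the D85-113 procedures on Table 7-1.
- **Section 6.2.1.4.1:** give the range by cohort: D85 to D113 per Table 7-1 for cohort Ia, and D85 to D110 per Table 7-3 for cohorts IIa/IIIa.

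Footnote c of Table 7-3 stays as it is. The cost is one footnote and one sentence, by amendment or a memo to sites. If cohort Ia has already finished cycle 2, a file note stating which schedule applied is enough for the review of missed or extra assessments. Nothing changes in the design, sample size or analysis.
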